#### **4.3.1.2 Duration of Fever**

Duration of fever will be summarized using descriptive statistics by treatment, as well as Kaplan-Meier plots. It is defined as the time from the start of treatment to return to afebrile state (tympanic temperature  $\leq 37.2$  °C) and remaining so for at least 21.5 hours. Patients who did not return to afebrile state will be censored at the last observation timepoint. Patients who are afebrile at baseline (tympanic temperature  $\leq 37.2$  °C) or whose body temperature is not collected will be excluded from the analysis.

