5.1 INCLUSION CRITERIA

Potential participants are eligible to be included in the study only if all of the following criteria apply:

- Signed Informed Consent Form (ICF)
A parent or authorized adult will be required to sign the ICF on behalf of the pediatric participant. The informed consent/assent of voluntary participation should be obtained in accordance with local requirements.
- Signed Assent Form when appropriate, as determined by participants' age and individual site and country standards
- Age 1 to <12 years at the time of signing ICF
- A participant who has a diagnosis of influenza virus infection and meets all the following conditions.
 - Fever $\geq 38^{\circ}\text{C}$ (tympanic temperature) at screening
AND
 - At least one of the respiratory symptoms of influenza virus infection (e.g., cough and nasal discharge/nasal congestion)
AND
 - A rapid influenza diagnostic test (RIDT) or polymerase chain reaction (PCR) shows positive for influenza A/B, e.g., point-of-care/local laboratory results with use of nasal aspirate, throat swab, or nasal drip/droplet (or other appropriate sample)
Results from local testing as part of standard of care are acceptable if samples are collected within 24 hours of screening and recorded in the participants' medical records.
- The time interval between the onset of symptoms and screening is ≤ 48 hours (the onset of symptoms is defined as the time when body temperature first exceeded 37.5°C if known, or the time when the first symptom was noticed by participant, parent, or caregiver)
- A participant who will be able to take baloxavir marboxil [REDACTED] for oral suspension or oseltamivir capsule for oral suspension/oral in the opinion of the investigator/sub-investigator
- A participant whose parent/guardian is willing and able to adhere to the study requirements in the opinion of the investigator/sub-investigator
- A participant who is able to adhere to the study requirements appropriately for the level of understanding

- PCR (–) or antigen test (–) for severe acute respiratory virus-coronavirus 2 (SARS-CoV-2) *using* point-of-care/local laboratory *test* with nasal aspirate, throat swab, or nasal drip/droplet (or other appropriate sample)

Results from local testing as part of standard of care are acceptable if samples are collected within 24 hours of screening and recorded in the participants' medical records.

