9.3.5.2 Summaries of Demographics and Baseline Characteristics

Demographics and baseline characteristics (including age, sex, parent/caregiver or self-reported race/ethnicity) will be summarized by treatment arm. Baseline data are the last data obtained prior to initiation of study treatment. Descriptive statistics (mean, standard deviation, median, and range) will be presented for continuous variables and counts and percentages will be presented for categorical variables.

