#### **4.2.2.5 Body Temperature**

Body temperature is collected in the patient diary 4 times daily for Day 1 -3, twice daily for Day 4 - 9 and once daily thereafter. Summary statistics of observation and the change from baseline in body temperature will be presented by treatment group for each recorded time point. Baseline is defined as the first recorded assessment after treatment on Day 1.

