#### **4.3.1.1 Time to Alleviation of Influenza Signs and Symptoms**

Time to alleviation of influenza signs and symptoms (TTAS) in hours, will be summarized using descriptive statistics by treatment, as well as Kaplan-Meier plots.

It is defined as the length of time taken from the start of treatment to the point at which all of the following criteria are met and remain so for at least 21.5 hours:

- A score of 0 (no problem) or 1 (minor problem) for cough and nasal symptoms (items 14 and 15 of the CARIFS questionnaire, see [Appendix 1](#)).
- A “yes” response to the following question on the CARIFS: “Since the last assessment has the subject been able to return to day care/school, or resume his or her normal daily activity in the same way as performed prior to developing the flu?”
- Return to afebrile state (tympenic temperature  $\leq 37.2$  °C).

If a score of 4 (“don’t know” or “not applicable”) occurs at any assessment for items 14 or 15, the assessment will not be included in the calculation of the alleviation of symptoms.

Patients who do not experience endpoint prior to completion or withdrawal from study will be censored at the last observation timepoint.

Baseline is defined as the first CARIFS assessment after start of treatment on Day 1.

Patients with symptom scores  $\leq 1$  for both items 14 and 15, as well as tympanic temperature  $\leq 37.2$ °C and a “yes” response to the question “Since the last assessment has the subject been able to return to day care/school, or resume his or her normal daily activity in the same way as performed prior to developing the flu?” at baseline will be excluded from the analysis.

The number of patients with completed CARIFS as well as the number with missing CARIFS per assessment, will be presented by treatment. Additionally, the number and percentage of those with “don’t know/not applicable” per question per assessment will be presented by treatment.

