#### **4.3.1.3 Duration of Symptoms**

Duration of symptoms is defined as alleviation of all symptoms as defined by a score of 0 [no problem] or 1 [minor problem] and remaining so for at least 21.5 hours, for all 18 symptoms specified in the CARIFS questionnaire.

Duration of symptoms will be summarized using descriptive statistics by treatment, as well as Kaplan-Meier plots.

If a score of 4 (“do not know” or “not applicable”) occurs at any assessment during the study for any item, with the exception of items 10, 11 and 12, the assessment will not be included in the calculation of the alleviation of symptoms. However, if a score of 4 occurs for items 10, 11 or 12, the assessment will be included, with a score of missing for these items, in which case the other non-missing items of the assessment will be used.

All patients will be included in the analysis, regardless of their symptoms at baseline.

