#### **4.3.1.4 Time to Return to Normal Health and Activity**

“Normal health and activity” is identified by a “yes” response to the following question on the CARIFS: “Since the last assessment has the patient been able to return to day care/school, or resume his or her normal daily activity in the same way as performed prior to developing the flu?”.

Time to return to normal health and activity will be summarized using descriptive statistics by treatment, as well as Kaplan-Meier plots.

Patients who do not return to normal health and activity will be censored at the last observation timepoint.

Patients in FASi will be removed from this analysis if a 'Yes' response to this item is reported at baseline.

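### SAP 4.3.1.1 and 4.3.1.2, read with the SAP's post-dose baselines, exclude children from the TTAS and fever analyses on readings taken after treatment has started

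*SAP*

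**What the plan says.** **Baselines.** For diary temperature, SAP 4.2.2.5 states: "Baseline is defined as the first recorded assessment after treatment on Day 1". For the symptom questionnaire, SAP 4.3.1.1 states: "Baseline is defined as the first CARIFS assessment after start of treatment on Day 1". No earlier diary value exists: Protocol 1.3 (Table 1, footnote i) limits Day 1 diary entries to the post-dose windows, and Protocol 8.1.1.1 places the first CARIFS after treatment.

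**Exclusions tied to baseline.**
- Duration of fever (SAP 4.3.1.2): "Patients who are afebrile at baseline (tympanic temperature" 37.2 °C or below) are left out, as are children with no temperature collected.
- TTAS (SAP 4.3.1.1): children with cough and nasal scores both at 1 or less, temperature at 37.2 °C or below and a yes to the normal-activity question "at baseline will be excluded from the analysis".
- Return to normal health and activity (SAP 4.3.1.4): "Patients in FASi will be removed from this analysis if a" yes answer is reported at baseline.

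**What sits beside them.** Duration of symptoms (SAP 4.3.1.3) does the opposite: "All patients will be included in the analysis, regardless of their symptoms at baseline". Protocol 9.3.3 uses the FASi (dosed, PCR-confirmed participants) for all efficacy analyses, and Table 1 of the SAP gives the same population. Elsewhere baseline is pre-dose: Protocol 9.3.5.2 says "Baseline data are the last data obtained prior to initiation of study treatment", and SAP 4.2.2.4 and 4.5.2 agree.

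**The concern.** Both the fever and TTAS clocks start at treatment. A child who is afebrile, or fully alleviated, at the first post-dose entry has reached that state while the clock was running, and may be having the event under study. Removing the child because of that reading is selection on a post-randomisation outcome.

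The fever rule is also stricter in one direction than the endpoint. Resolution must last 21.5 hours to count as an event, yet a single reading is enough to exclude. Acetaminophen is permitted from Day 1 (Protocol 6.1.3 and 6.8.1), and rescue medication is handled by a treatment-policy strategy. Even so, one suppressed reading would remove a child whose fever later returns.

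At stake are the medians and Kaplan-Meier curves, which are the main output for these endpoints. No supplementary analysis in SAP 4.3.1.1 restores the excluded children. The post-dose anchor also reaches the change-from-baseline summary of temperature in 4.2.2.5, which sits under the primary safety analysis.

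**Working it through.** The plan gives no figure for the share excluded. Its only design calculation concerns the chance of seeing an adverse event and does not bear on this point. The check is therefore a reading of the rules, followed by an illustration under stated assumptions.

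**Step 1. Which baseline applies in 4.3.1.2?**
- *Post-dose (4.2.2.5, the only temperature-specific definition).* Protocol 5.1 requires at least 38 °C at screening, so an eligible child at or below 37.2 °C has changed since screening. The exclusion then depends on events after screening or dosing.
- *Pre-dose (the general definition in 4.5.2).* Every eligible child was at 38 °C or above at screening, so the exclusion is essentially empty.

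On the first reading the rule selects on outcome. On the second it does almost nothing. The TTAS rule also requires 37.2 °C or below, and 4.3.1.1 states a post-dose baseline outright.

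**Step 2. Effect on one arm's median, if those dropped are the fastest resolvers.** Assume exponential times with median M. After dropping the fastest share q, the median of those kept is M × [ln 2 − ln(1 − q)] / ln 2. Take M = 40 h (assumed) and the planned 67 and 33 children; the FASi size is not given, so these counts are ceilings.

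| q (assumed) | Median kept | Change | Kept (baloxavir / oseltamivir) |
|---|---|---|---|
| 5% | 43.0 h | +7% | 64 / 31 |
| 10% | 46.1 h | +15% | 60 / 30 |
| 15% | 49.4 h | +23% | 57 / 28 |
| 20% | 52.9 h | +32% | 54 / 26 |

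For q = 10%: (0.693 + 0.105) / 0.693 = 1.15. The shape matters: with Weibull times of shape 1.5 the ratio is raised to the power 1/1.5, giving +5% to +20% over the same range of q.

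**Step 3. Effect on the comparison when both arms are cut at the same time.** For exponential times, dropping everyone resolved by time t₀ gives a kept median of M + t₀. Assume true medians of 35 and 45 h (difference 10 h, ratio 0.78).

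| t₀ | Excluded | Medians kept | Difference | Ratio |
|---|---|---|---|---|
| 4 h | 7.6% / 6.0% | 39 / 49 h | 10 h | 0.80 |
| 8 h | 14.7% / 11.6% | 43 / 53 h | 10 h | 0.81 |
| 12 h | 21.2% / 16.9% | 47 / 57 h | 10 h | 0.82 |

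**Step 4. Effect when the excluded shares do not match the underlying course.** Suppose there is no true difference (40 h in both arms), but 15% are dropped on baloxavir and 5% on oseltamivir. The medians become 49.4 and 43.0 h, a spurious gap of 6.4 h; reversing the shares reverses the sign.

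**Step 5. Brief suppression.** If a dropped child's fever returns, that child is not a fast resolver and may be a slow one. Removing slow resolvers shortens the median, so the bias can go either way.

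**The case against.** Four points on the other side have force.

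1. *Baseline in 4.3.1.2 is inferred.* The temperature definition sits in the safety section, and the general definition is pre-dose. This stands. The post-dose reading is the more likely one because it is specific to temperature, but the SAP must say which it means.
2. *A reader might infer that no child can be afebrile before dosing.* The documents do not support that. Table 1 of the protocol and its footnote a allow screening on the day before Day 1, so some children could have cleared by the time of dosing.
3. *A reader might infer that the rule erases a real treatment effect.* An example can be built to do so. Let 20% on baloxavir and 10% on oseltamivir clear at 4 h, with everyone else taking 4 h plus an exponential time of median 24 h. The full medians are 4 + 24 × log₂(1.6) = 20.3 h and 4 + 24 × log₂(1.8) = 24.4 h, and both become 28.0 h after exclusion. That follows because the whole effect was placed at the first reading. No figure in the documents supports those shares, and Step 3 shows little change under a more ordinary course.
4. *The three rules are not alike.* TTAS exclusion needs all criteria together at the first entry, so it should remove far fewer children than the fever rule. For return to activity there is no pre-dose CARIFS, and a yes at the first entry may describe a child who was never limited. Counting that child as an event is a debatable choice.

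The protocol does leave data-handling conventions to the SAP, which weakens any charge that the protocol was breached. It does not explain why the SAP's own estimand population is narrowed by a post-dose reading.

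**Conclusion.** The fever and TTAS exclusions should be changed. With the SAP's post-dose baselines they select on what happened after screening or dosing and depart from the FASi. If a pre-dose temperature baseline was intended, the fever exclusion is essentially empty and can go without loss.

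The size and direction of the bias cannot be computed from the documents. The 7–32% lengthening of a median assumes exponential times, an excluded share of 5–20%, and that those dropped are the fastest resolvers. Brief suppression would pull the figure down or reverse it. Exclusion at a common time barely changes the ratio between arms; unequal exclusion can mask or create a difference, and with only 67 and 33 children planned a few exclusions count. The effect on TTAS is probably small.

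These are secondary, descriptive endpoints without hypothesis tests, adverse-event summaries are untouched, and duration of symptoms already keeps everyone. This is a should-fix.

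**What to change.** - **4.3.1.1 and 4.3.1.2:** analyse all FASi children with data. Count the event at the first qualifying post-dose assessment that is sustained for 21.5 hours. A child who qualifies at the first entry and stays so has the event there; a child whose fever returns has it later.
- **4.2.2.5 and 4.3.1.2:** define temperature baseline as the last pre-dose tympanic temperature. It is already collected with the screening vital signs (Protocol 1.3 and 8.2.2), although for some children it may date from the day before dosing.
- **Reporting:** give the number per arm who meet the current exclusions, and keep the analysis with those exclusions as a sensitivity analysis.
- **4.3.1.4:** present an all-FASi analysis alongside the current one, since neither is clearly right without a pre-dose questionnaire. The individual-symptom supplementary analysis in 4.3.1.3 has a comparable exclusion and can be reviewed at the same time.

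The cost is SAP wording and programming, with no new data collection. Reported medians may become shorter.

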#### **4.3.1.3 Duration of Symptoms**

Duration of symptoms is defined as alleviation of all symptoms as defined by a score of 0 [no problem] or 1 [minor problem] and remaining so for at least 21.5 hours, for all 18 symptoms specified in the CARIFS questionnaire.

Duration of symptoms will be summarized using descriptive statistics by treatment, as well as Kaplan-Meier plots.

If a score of 4 (“do not know” or “not applicable”) occurs at any assessment during the study for any item, with the exception of items 10, 11 and 12, the assessment will not be included in the calculation of the alleviation of symptoms. However, if a score of 4 occurs for items 10, 11 or 12, the assessment will be included, with a score of missing for these items, in which case the other non-missing items of the assessment will be used.

All patients will be included in the analysis, regardless of their symptoms at baseline.

#### **Supplementary Analyses**

In the main analysis of the duration of symptoms, only complete assessments (i.e., assessments that have responses for all 18 symptoms in the CARIFS questionnaire) that do not contain a score of 4 for any items, with the exception of items 10, 11, and 12, are considered. A supplementary analysis will be conducted that considers all assessments in the calculation of the duration of symptoms, where a score of 4 does not break the incidence of alleviation for items other than 10, 11, and 12, and a score of 4 is considered alleviation for items 10, 11, and 12.

In addition, duration of individual symptoms will be summarized using descriptive statistics by treatment. Patients who have an individual symptom score  $\leq 1$  or missing at

baseline or whose individual symptom score are all missing will be excluded from the analysis.

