## 1.2 STUDY DESIGN

This is a multicenter, randomized, open-label, active-controlled (i.e., oseltamivir) study to assess the safety, pharmacokinetics, and efficacy of baloxavir marboxil compared with oseltamivir in Chinese pediatric participants aged 1 to  $<12$  years with influenza symptoms within 48 hours of symptom onset.

Approximately 100 pediatric participants are planned to be enrolled. Of the overall sample size, approximately 1/3 participants who are 1 to  $<5$  years old and 2/3 participants who are 5 to  $<12$  years old are planned to be enrolled.

Participants will be screened and randomized on Day 1 and assigned in a 2:1 ratio to receive a single oral dose of baloxavir marboxil based on body weight (2 mg/kg for participants weighing  $<20$  kg or 40 mg for participants weighing  $\geq 20$  kg to  $<80$  kg or 80 mg for those weighing  $\geq 80$  kg) for oral suspension or oseltamivir (twice a day dose based on body weight) for 5 days. Re-screening of participants who fail to meet the inclusion and exclusion criteria will not be permitted for the same illness.

episode, as the time from symptom onset to the treatment window is limited to 48 hours. Either drug will be started at the time of randomization.

The total study duration for each participant will be 29 days, consisting of a 5-day treatment period (mandatory visits on Days 1, 2, and 4) and a 24-day follow-up period (mandatory visits on Days 6, 10, and 29). For the following assessments at clinic visits: physical examinations, vital signs, adverse events, concomitant therapies, clinical laboratory tests, and nasal/throat swabs. Visits on Day 29 or early termination visits can be conducted remotely. Throughout the treatment follow-up periods, the parents/caregivers will maintain a participant diary for each participant in order to record body temperatures (tympanic assessment), influenza symptoms, and acetaminophen use.

Temperatures will be recorded as follows:

- Days 1–3: 4 times daily (morning, noon, evening, and bedtime);
- Days 4–9: twice a day (morning and evening);
- Days 10–15: once daily.

Influenza symptoms will be recorded as follows:

- Days 1–9: twice a day (morning and evening)
- Days 10–15: once a day.

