#### **Supplementary Analyses**

In the main analysis of the TTAS, only complete assessments (i.e., assessments that have responses for items 14 and 15 of the CARIFS questionnaire, the normal daily activity question and temperature) that do not have scores of 4 for items 14 and 15 are considered in the calculation of the TTAS. A supplementary analysis will be conducted that considers all assessments in the calculation of the TTAS, where a score of 4 for items 14 or 15 does not break the incidence of alleviation.

Another supplementary analysis will be conducted in which the following criterion will be removed from the calculation of the TTAS:

- A “yes” response to the following question on the CARIFS: “Since the last assessment has the subject been able to return to day care/school, or resume his or her normal daily activity in the same way as performed prior to developing the flu?”

In addition, analyses based on virus type and subtype may be conducted if there are a sufficient number of patients with each type/subtype.

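### In the main analyses of symptom duration and TTAS, an incomplete diary form is left out even when it records a relapse, so some children are dated recovered too early

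*SAP*

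**What the plan says.** **Endpoint.** SAP 4.3.1.3 defines duration of symptoms by scores of 0 or 1, "remaining so for at least 21.5 hours, for all 18 symptoms specified in the CARIFS questionnaire".

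**Scores of 4.** If an item other than 10, 11 or 12 is scored don't know/not applicable, "the assessment will not be included in the calculation of the alleviation of symptoms". For items 10 to 12 the SAP is more lenient: "the assessment will be included, with a score of missing for these items", and the answered items are still used.

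**Blank items.** The Supplementary Analyses paragraph of 4.3.1.3 describes the main analysis as using "only complete assessments (i.e., assessments that have responses for all 18 symptoms in the CARIFS questionnaire".

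**TTAS.** The corresponding paragraph of 4.3.1.1 limits the main analysis to "only complete assessments (i.e., assessments that have responses for items 14 and 15 of the CARIFS questionnaire, the normal daily activity question and temperature", again with no 4 on items 14 or 15.

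**Supplementary analysis.** "A supplementary analysis will be conducted that considers all assessments in the calculation of the duration of symptoms", with a 4 not breaking alleviation. TTAS has a similar one.

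**Schedule and reporting.** CARIFS is completed on "Days 1–9: twice a day (morning and evening", then once daily to Day 15 (SAP 1.2). For completeness, "The number of patients with completed CARIFS as well as the number with missing CARIFS per assessment, will be presented by treatment"; don't-know answers are tabulated as well.

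**The concern.** An incomplete form can be of two kinds. If every recorded answer is 0 or 1, the missing item leaves the child's status unknown, and setting the form aside is reasonable. If any recorded item is 2 or 3, the status is known: not all 18 symptoms are at 0 or 1, whatever the missing answer would have been. The main analysis treats both kinds alike and removes them.

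For TTAS, a form with cough scored 3 but no temperature is removed in the same way. So is one with a temperature above 37.2 °C, or a 'No' to the activity question, if another component is missing.

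The endpoint requires alleviation to persist. With two forms a day, same-time forms on consecutive days are 24 h apart, which exceeds 21.5 h, and only one form lies between them. Removing that one form can hide a relapse that the diary records, and the child's event time is then wrong by the endpoint's own definition.

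**Working it through.** The plan gives no figure that depends on this rule, so there is none to reproduce. The rule was applied first to constructed diaries and then to simulated ones.

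**Worked example.** Assumed: dose at 10:00 on Day 1, diary forms at 08:00 and 18:00. Hours from dose are then 3 × 24 − 2 = 70 (Day 4 morning), 80 (Day 4 evening), 94 (Day 5 morning), 104 (Day 5 evening), 118 (Day 6 morning) and 128 (Day 6 evening). The child is symptomatic through Day 3 evening and well at 70 h.

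1. *One relapse form:* at 80 h one item is major and another required item is blank or 4; the child is well from 94 h. Literal rule: the 80 h form is passed over, 94 − 70 = 24 ≥ 21.5, event at 70 h. Relapse counted: the period restarts at 94, 118 − 94 = 24, event at 94 h. Error: 94 − 70 = 24 h early.
2. *Two relapse forms (80 h and 94 h):* literal rule, 104 − 70 = 34 ≥ 21.5, event at 70 h. Relapse counted: restart at 104, 128 − 104 = 24, event at 104 h. Error: 104 − 70 = 34 h early.
3. *Same relapse as in 1, on a complete form:* both rules give 94 h. The error needs an incomplete form.
4. *No relapse, but the first well form (70 h) is incomplete:* it cannot start the period, so the literal rule gives 80 h. A complete diary gives 70 h. Error: 10 h late.

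**How often.** The documents give neither the rate of incomplete forms nor the rate of relapse after first alleviation, so both are assumed. Simulation: 20,000 children per cell, the schedule above, recovery at 24 h plus an exponential time with mean 90 h, relapse probability per form decaying over 48 h from the starting value shown, incompleteness at random. Cells show the percentage dated too early by the literal rule compared with counting recorded failures, with the median shift.

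| Starting relapse probability | 2% incomplete | 5% | 10% | 20% |
|---|---|---|---|---|
| 5% | 0.1% (29 h) | 0.2% (24 h) | 0.6% (34 h) | 0.9% (34 h) |
| 15% | 0.2% (34 h) | 0.8% (34 h) | 1.5% (34 h) | 3.1% (34 h) |
| 30% | 0.5% (34 h) | 1.6% (34 h) | 2.9% (34 h) | 5.6% (38 h) |

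The median time was the same under both rules in 11 of the 12 cells. In the other it moved by one diary step (104 h against 118 h). In the same runs the literal rule dated about 2%, 5%, 10% and 19% of children *later* than using all forms, through the mechanism in example 4.

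**Second set of assumptions.** Forms every 12 h to Day 9 then daily; lognormal recovery with median 130 h and log-scale SD 0.45; 15% or 30% failing forms in the first 36 h after recovery; 5–20% incomplete. About 1–6% of children were dated early, by about 30–34 h on average, and about 5–19% late. Compared with complete diaries the net mean shift was later, from about 0.3 h at 5% incomplete to about 2 h at 20%. The median was identical under the written rule and the fix. The fix removed every early misdating. At 10% incomplete it lowered the mean absolute error from about 2.5 h to about 1.7 h.

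**The case against.** **The gap rule is unstated.** The SAP does not say how a set-aside form counts toward the 21.5 hours. Its supplementary analyses are distinguished by a 4 not breaking alleviation, which could imply that in the main analysis it does. On that reading the early dating disappears (94 h in example 1). This is possible, but the text says excluded forms are not part of the calculation, which points to passing over them. A sentence is needed on either reading.

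**The supplementary analyses restore the relapse.** They do, giving 94 h in example 1. They also change how a 4 is treated and do not say how blanks are handled, so a difference from the main result could not be traced to this rule. They are also not the main result.

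**The rule works in both directions.** This stands. A reader might infer that it shortens symptom duration overall. The documents do not support that: the same sentences drop well but incomplete forms, and under the second set of assumptions the net mean shift is toward later recovery.

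**Bias between arms.** A reader might also infer a spurious drug effect, since the trial is open-label and uses paper diaries (Protocol A5–1). Nothing in the documents indicates that completeness will differ by arm. The diary schedule is common to both, and the counts by treatment would reveal a difference. Nor is it sound to set a shift in the mean against the medians quoted in Protocol 2.3 (138.1 and 150.0 hours): the planned summary here is Kaplan-Meier plots and the median, and those figures belong to a differently labelled endpoint.

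**Conclusion.** The point holds as an error in individual event times. As written, the main derivation can date a child as recovered across a relapse recorded in that child's own diary, contrary to the endpoint's persistence requirement. The size is 24 h or 34 h in the worked examples. It is about 30 h for roughly 1–6% of children if 5–20% of forms are incomplete at random and 15–30% of early post-recovery forms show relapse; with fewer of either it is rarer. These rates are assumptions, not figures from the documents.

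The effect on arm summaries is small: medians are essentially unchanged and the net mean bias has no fixed sign. Both endpoints are secondary and descriptive, so no error rate or sample size is affected. The change is worth making because the rule discards decisive evidence and is cheap to correct, not because a treatment comparison is at risk.

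**What to change.** - **SAP 4.3.1.3:** state that an assessment with any recorded score of 2 or 3 counts as not alleviated, even if other items are blank or scored 4.
- **SAP 4.3.1.1:** state the same for a cough or nasal score of 2 or 3, a 'No' to the activity question, or a temperature above 37.2 °C, even if another component is missing.
- **Both sections:** set aside only assessments whose recorded answers are all compatible with alleviation, and state how the resulting gap counts toward the 21.5 hours.

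The cost is a few SAP sentences and a few lines of programming, with no new data. A few durations become longer. Well but incomplete forms still cause some late dating, which this change does not address; the planned supplementary analyses remain useful for that.
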